Middle School Cluster RCT to Evaluate E-Cigarette Prevention Program: CATCH My Breath

NCT04843501

Version Date: 7/21/2021

Protocol for Middle School Cluster RCT to Evaluate E-cigarette Prevention Program: CATCH My Breath

Protocol Title: Middle School Cluster RCT to Evaluate E-cigarette Prevention Program: CATCH My Breath

Principal Investigator: [name]

Co-Investigators: [name]; [name]; [name]; [name]; [name]

Study Coordinator: TBD

Population: 30 schools across the Texas

Number of Sites: Single Site: UT School of Public Health - Austin Regional Campus

Study Duration: September 1, 2018-August 30, 2023

Subject Duration: September 1, 2019 - August 30, 2022

General Information

The primary purpose of this study is to empirically assess the three year effects of the CATCH My Breath (*CMB*) program on delaying the onset of e-cigarette use with a 6th-8th grade cohort, using a 30-school group randomized controlled trial (RCT), with 2,400 students. The *CMB* curriculum is divided into four sessions lasting approximately 20-30 minutes each. A variety of educational strategies are used and include cooperative learning groups, large group discussions, interviews, role-play, media, reports, and goal setting.

The *CMB* program is based on well-established educational best practices and empirical evidence, and has been piloted tested for feasibility; feedback on the pilot program was received from 42 teachers and 2,255 6th - 8th grade students. Pilot test results were largely favorable, and the program was revised based on findings from the pilot study. *CMB* is ready for a larger, RCT with teachers and students.

Our ultimate goal is to bring scientifically accurate information to inform and educate teachers, parents and health professionals in the school/afterschool setting about the health risk of e-cigarettes. Our aim is to equip students with answers about e-cigarettes and to make informed decisions about the use of e-cigarettes.

E-cigarette use is epidemic among middle school children, and schools have few rigorously prepared resources to educate students and families. [name] is one of several scientific editors of the 2016 Surgeon General Report on E-cigarette Use among Youth and Young Adults and is well versed in the health effects of e-cigarettes. Our goal is to rigorously evaluate the *CMB* program in order to provide educational agencies evidence-based resources to coincide with the recently released Surgeon General Report.

Background Information

E-cigarette consumption among youth is of concern because of the harmful effects of nicotine on human growth and development in terms of addiction and brain development, and fetal development among pregnant teenagers. The rapid increase in use among teens is of concern and portends the possibility of nationwide health consequences. The epidemic calls for a coordinated and scientifically accurate response.

CMB will utilize the gold standard RCT approach to evaluate the effectiveness of the intervention. We will evaluate *CMB* using a cluster group randomized trial design comparing 15 usual care schools implementing Texas Education Agency required tobacco prevention objectives to 15 schools implementing the *CMB* program. We intend to measure children before and after implementation of the program to assess changes in knowledge, attitudes and intentions to use e-cigarettes. We will assess students with a brief survey tool, assess student likes and dislikes, judge the length of time to implement the curriculum, and assess teacher reactions to teaching the program. The effectiveness of *CMB*, and user experience, will be assessed mixed method qualitative and quantitative approaches, including: (a) the impact of *CMB* on student susceptibility to use e-cigarettes; (b) the impact of *CMB* on initiation of e-cigarette use (ever use); (c) the impact of *CMB* on intermediate program outcomes (such as harm perceptions, outcome expectations, self-efficacy); and (d) the feasibility, fidelity and dose of program implementation.

CMB is a *best-practice* based program that was modeled after an *evidence-based* program called the Class of 1989 Study and elements from the Coordinated Approach to Child Health (CATCH) Program. Both the Class of 1989 and CATCH were NIH-funded studies, and both have statistically reliable research results. The Class of 1989 formally studied two communities and a school-based tobacco prevention program, which showed strong effects in reducing student smoking from 6th to 12th grade. CATCH studied children in 3rd to 8th grades and showed strong effects in improving student dietary intake and physical activity, and in later versions of the program, effects on child obesity. *CMB* was modified from the Class of 1989 tobacco prevention program and designed to be added to the CATCH portfolio of school health programs. The same study teams that worked on Class of 1989, and CATCH, have created the *CMB* program.

CMB is also informed by new scientific literature on the rise in use of e-cigarettes in the United States, and the emerging science regarding the harmful consequences of e-cigarette use by preteens and teens.

Objectives

The objective of this study is to evaluate the effectiveness of an E-cigarette curriculum for middle school. The overall goal of *CMB* is to prevent E-cigarette use among adolescents. This study will be guided by the following aims:

Aim 1. Quantify the direct program effect on susceptibility and first use of e-cigarettes on a cohort of children exposed to the *CMB* program in 6th, 7th, and 8th grades, compared to same-aged students in usual care schools.

Hypothesis 1: After three school years of exposure to the *CMB* school-based prevention program, 8th-grade students in 15 intervention schools will report: (a) lowered susceptibility to use e-cigarettes; and (b) lowered first time (ever) use of e-cigarettes compared to students in 15

comparison schools.

Aim 2. Quantify the mediating effects of intermediate program outcomes (such as intentions to use, resistance skills, self-efficacy, and media literacy) to understand the mechanisms by which program effects occur.

Hypothesis 2: After three school years of exposure to the *CMB* school-based prevention program, 8th-grade students in the 15 intervention schools will improve scores on intermediate program outcomes compared to students in the 15 comparison schools.

Secondary Aim. Given the longitudinal study design and large number of student participants, we also intend to examine important secondary hypotheses to understand the nature of the e-cigarette epidemic, including nicotine addiction, transition to combustible tobacco use, and e-cigarette assisted marijuana use.

We will also assess students knowledge, attitudes and possible experience with tobacco and e-cigarettes before and after they receive *CMB* through a pre-post survey. A subset of students, parents, and teachers will be invited to participate in focus groups to gather input for continuous quality improvements to the program and online delivery system.

Study Design

We will evaluate *CMB* using a cluster group RCT design comparing 15 usual care schools implementing Texas Education Agency required tobacco prevention objectives to 15 schools implementing the *CMB* program (a total of 30 schools). Thirty schools will be recruited from a pool of 188 public middle schools within 100 miles of The University of Texas School of Public Health in Austin, matched by key demographic variables (percent male and female, percent free and reduced lunch, percent race and ethnicity, percent English as second language) and randomized into intervention and comparison conditions. To ensure comparability, we will recruit 15 matched pairs of schools and randomize them into either treatment or control usual care conditions.

There are no known risks associated with this study. The potential benefits include equipping adolescents with the appropriate knowledge and refusal skills for e-cigarettes.

Study Population & Procedures

The project will identify 30 Texas schools (at least one teacher and/or class per school) to evaluate the effectiveness of four developmentally appropriate e-cigarette lessons (approximately 20-30 minutes long) for middle school aged youth (6th 8th grade). Consistent with the RCT design, we will randomize 15 usual care schools and 15 schools with *CMB* school-based prevention program with cluster size 80 in each school (total sample size = 2,400). We will exclude schools that have participated in our previous 2 pilot tests, or are currently implementing *CMB*.

The study team will draw a convenience sample from interested schools, who will then be matched and assigned to study conditions. School matching will be based on data available through the Texas Education Agency (TEA) online database and will include: the size of school, percent free and reduced price lunch, percent limited English proficiency, percent midyear student transfers, percent staff in school with less than five years experience, percent staff leaving midyear, percent passing state mandated reading and math tests, and attendance rate.

A recruitment presentation, directed at the principal and a curriculum committee or another decision-making committee, will be delivered to interested schools. School recruitment and randomization will be done in Year 1 (July 18 June 19). Implementation of the curriculum will occur in Years 2-4 (Fall 19 Spring 22). Data analyses, presentations and manuscript developing will be ongoing in Years 2-5. We will obtain a Memorandum of Understanding (MOU) from each participating school which delineates responsibilities of the school and research team. Active parental consent will be obtained at back-to-school parent nights by inclusion of consent forms in the school packet of forms that parents sign at the beginning of the school year. For parents not in attendance, students will receive a recruitment packet to take home in the schools weekly take-home folder. Small incentives to schools (\$500 stipend for a site coordinator) and students (\$15-\$20 for t-shirts, water bottles, etc) greatly facilitate return of consent forms, recruitment and retention.

CMB will provide study materials to teachers and schools through a state-of-the art online delivery portal. Teachers will access *CMB* program materials and resources through the CATCH digital access portal (www.digitalcatch.org), built with Ruby on Rails, a highly scalable, efficient and popular web application framework. A site based management team will oversee program implementation. Teachers will be trained via webinar. Project staff will visit all participating schools to assemble and train the CATCH site-based management team, and answer questions about the study. Teachers in *CMB* intervention schools will be provided with *CMB*-specific training for implementing the lessons with fidelity through a one-hour live webinar with [name], which will be offered at multiple times to accommodate teaching schedules.

All student assessments (1 pre-test and 5 follow-up tests) will be conducted online to improve reliability and validity of the survey. Online assessments offer a variety of strengths including utilizing skip patterns, which decrease survey burden; presenting pictures of the products, which increases validity; and providing increased confidentiality in answers that paper surveys cannot provide. In addition to basic demographic information, data will be collected on e-cigarette use behaviors, susceptibility to e-cigarettes, addiction to and dependence on nicotine and e-cigarettes; risk perceptions, reasons to use or not to use, perceived prevalence, normative beliefs, outcome expectations, self-efficacy to resist use (intermediate outcomes); and additional covariates and exploratory factors that include peer and parental use of tobacco products, other tobacco use behaviors, and marijuana and alcohol use behaviors.

CMB will also provide assessment to teachers and site coordinators at both intervention and at usual care schools to measure implementation of the *CMB* program and usual care program. All teacher and site coordinator assessment will be conducted online to improve reliability and validity of the survey. The online questionnaire will collect data on basic demographic; what program was taught (usual care schools) and validate the *CMB* program in the intervention schools; how the program was taught (as directed), how well the program was taught (training involved) and exploratory factors on the implementation of the programs taught in both intervention and usual care schools. This assessment will be done every school year of implementation.

Data and Safety Monitoring

No adverse events are expected. Unanticipated problems, to include protocol deviations, will be reported to the PI and IRB. Staff will receive training, certification, and retraining in consent procedures and data collection procedures to assure accurate information and confidentiality. The survey tool is very short and we anticipate will be completed by students in less than 8 minutes.

Data Collection and Management: Research Electronic Data Capture (REDCap) was designed through NIH funding, specifically to provide research institutions with the ability to collect, house and process data in a secure platform. REDCap has Zone 100 security which is accepted by The University of Texas Health Science Center (UTHSC) to adhere to Health Insurance Portability and Accountability Act (HIPAA) and Federal Information Security Management Act (FISMA) compliance standards and is accessible from anywhere with Internet capability and useable offline on Android and iOS mobile devices. Along with offering a high level of security, REDCap also provides many advanced features such as branching logic, calculated fields, and file uploading as well as fully formatting data export directly into all of the major statistical packages. The data manager will utilize computer software to detect errors in the data files such as skip pattern error, duplicate or incorrect identification numbers, and inconsistent responses. To assure security of study data, weekly backup copies of the master file will be made and stored in a physically remote secure area.

Statistics

From each of the 30 schools, we will recruit 80 6th-grade students, for a total n=1,200 per study condition and 2,400 total students. Follow-up measurements will be conducted post-intervention in spring in 6th, and spring and fall in 7th and 8th grades, for a total of 6 measurements per student.

Statistical analysis will follow state of art cluster randomized trial methodology. The statistical analysis will be conducted in four phases: (1) Descriptive Analysis, (2) Analysis of Aim 1, (3) Analysis of Aim 2, and (4) Secondary Exploratory Analyses.

(1) Descriptive Analysis will be conducted with baseline data to produce a profile of demographics and baseline characteristics. Analysis will consist of descriptive statistics such as frequencies, means, cross-tabulations and graphical representation of data. Results will provide information on imbalances between treatment groups that should be accounted for in the confirmatory analysis.

(2) Analysis of Hypothesis 1 is to test the proposed hypothesis that after three years exposure to the *CMB* school-based prevention program, 8th grade students in the intervention schools will report lower a) susceptibility to use e-cigarettes and b) ever e-cigarette use prevalence compared to students in the comparison schools. Multi-level regression models will be used to test for intervention effects while controlling for baseline differences through the use of covariates. Three-level hierarchical models will be used to assess the impact of the intervention where level 1 is the repeated measurement of individual students, level 2 is the student, and level 3 is the school. Multi-level models provide a powerful and flexible framework for the analysis of repeated measures data in the presence of possible cluster effects, allowing for the inclusion of subjects with incomplete data, thus maximizing power and minimizing the Type I error rate.

(3) Analysis of Hypothesis 2 is to test the hypothesis that after three years exposure to the *CMB* school-based prevention program, 8th grade students in the intervention schools will improve scores on intermediate program outcomes compared to students in the comparison schools. Treating these variables as outcomes, we will employ the same statistical strategies as described in analysis of Aim 1. In addition, we will also analyze these intermediate variables as mediators of program effect to determine which act as a mechanism for explaining the effect of the intervention on the two primary outcomes (susceptibility and ever use). These analyses will allow further examination of these possibilities, and will build on the multi-level models developed for the analyses described in Aim 1.

(4) Secondary Exploratory Analyses. Given the longitudinal study design, we intend to examine

important secondary hypotheses to understand the nature of the e-cigarette epidemic with the respect to nicotine dependence and progression to combustible tobacco, marijuana, and alcohol use. Multi-level regression models will be used to assess the longitudinal relationships between independent and dependent variables, while controlling for intervention effects, and baseline differences through the use of covariates.

Ethics, data handling and record keeping

For the school personnel questionnaires, consent will be inferred with the completion of each questionnaire. A coversheet will be attached to each survey describing the purpose, risks, and benefits of the self-report surveys. A personal identification number will be assigned to each survey participant to maintain anonymity. After the final confirmation at the end of the study, the names associated with the identification numbers will be destroyed. For the student measures, each student will receive a recruitment packet to take home to parents or guardians. Active parental consent will be obtained at parent back to school night by inclusion of consent forms in the school packet of forms that parents sign in the beginning of the year. Students will be assigned a personal identification to maintain anonymity. The names associated with the identification numbers will be destroyed after the final confirmation at the end of the study. No personal identification information (e.g., name, address, etc.) will be reported in any manuscript.

Confidentiality of all subjects will be fully protected. All study records will be kept in locked file cabinets and secured computer files. Only aggregate data will be reported and released, and at no time will individual names appear in any report/article related to the study.

Quality control and assurance

All data will be collected and stored in secure rooms with secure computers following the UTHealth data storage and retrieval protocols, and the Michael & Susan Dell Center. Access to data will be managed by [name].

Publication Plan

We intend to publish at least one publication reporting the effectiveness of the *CMB* program. Participating schools will be given no-cost copies of the program for their future use and a copy of the pilot test report. Results will be reported in aggregate.

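### Does parental consent after school randomisation, with baseline covariates left unnamed, call for a change to the Aim 1 analysis?

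*Combined protocol and SAP*

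**What the plan says.** All references are to the combined protocol and SAP.

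- **Timing.** Study Population & Procedures states "School recruitment and randomization will be done in Year 1", a window running from July 2018 to June 2019, and "Implementation of the curriculum will occur in Years 2-4", beginning in fall 2019. The title information gives "Subject Duration: September 1, 2019 - August 30, 2022" and "Version Date: 7/21/2021".
- **Consent.** Study Population & Procedures states "Active parental consent will be obtained at back-to-school parent nights by inclusion of consent forms in the school packet of forms", with a take-home packet for parents who do not attend. The ethics section repeats this route and ties the packet to the student measures. Neither section distinguishes the arms.
- **Matching.** "School matching will be based on data available through the Texas Education Agency (TEA) online database". These are school-level variables.
- **Baseline data.** "All student assessments (1 pre-test and 5 follow-up tests) will be conducted online". The survey covers e-cigarette use and susceptibility, and "additional covariates and exploratory factors that include peer and parental use of tobacco products".
- **Analysis.** Under Statistics, the descriptive analysis is to inform which baseline imbalances the confirmatory analysis takes into account. The analysis of Hypothesis 1 uses three-level models (repeated measurement, student, school) and controls for baseline differences with covariates that it does not list.

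**The concern.** Randomising schools makes the arms comparable only if students then join the cohort independently of their school's arm. Here consent comes after assignment, and intervention schools must know their arm at about the same time because they start teaching the curriculum that fall. If intervention schools promote the study harder, or if families respond differently once they know the arm, the two cohorts could differ in underlying risk before any lesson is taught. School-level matching cannot prevent that, because it does not govern which families within a school consent.

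Baseline adjustment is then the main protection left, and it is loosely specified. The covariates are not named, observed imbalance may guide their choice, and the pre-test could be either a covariate or the first of the six repeated outcomes. At stake would be a biased estimate for susceptibility and ever use, together with some freedom in choosing the primary model.

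**Working it through.** **1. Order of events.** Randomisation ends in June 2019, and students enter from 1 September 2019 on forms signed at the start of the school year. No sentence states the order outright, but the dates put consent after assignment. The body of the document contains no step that withholds the arm. The consent pages are not in our copy, so what families were told cannot be checked.

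**2. The plan's own figures.** 15 × 80 = 1,200 students per arm, 30 × 80 = 2,400 in total, and 1 pre-test + 5 follow-ups = 6 measurements. All agree with the text. The plan gives no alpha, event rate, ICC or consent rate, so the size of any selection bias cannot be derived from it. Every input in steps 3 to 5 except the cluster size and the numbers of students and schools is an assumption.

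**3. Unadjusted illustration, no true effect.** Assume 40% higher-risk students, with 8th-grade ever use of 35% in them and 10% in the rest, and ICC 0.02.

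- Overall prevalence: 0.4 × 0.35 + 0.6 × 0.10 = 0.20.
- Bias = gap in higher-risk share × (0.35 − 0.10). Gaps of 2, 5 and 10 points give 0.5, 1.25 and 2.5 points.
- Design effect = 1 + 79 × 0.02 = 2.58.
- SE = √(2 × 0.20 × 0.80 × 2.58 / 1,200) = 2.62 points.
- False-positive rate (noncentral t, 30 − 2 = 28 df, two-sided 5%): 5.4%, 7.5% and 15.1%.

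Varying one input at a time:

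| Input varied | 2-point gap | 5-point gap | 10-point gap |
|---|---|---|---|
| ICC 0.05 to 0.01 | 5.2-5.6% | 6.3-8.6% | 10.2-19.7% |
| Higher-risk ever use 25% to 45% | 5.2-5.7% | 6.0-9.3% | 9.3-22.7% |
| Higher-risk share 50% to 20% | 5.4-5.5% | 7.3-8.1% | 14.3-17.8% |

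**4. With adjustment, which is what the plan proposes.** Take four binary pre-test covariates: susceptibility, ever use, peer tobacco use and parental tobacco use. Their assumed frequencies in higher-risk students and the rest are:

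| Covariate | Weak markers | Strong markers |
|---|---|---|
| Susceptibility | 50% / 20% | 70% / 15% |
| Ever use | 5% / 1% | 15% / 3% |
| Peer use | 40% / 20% | 60% / 15% |
| Parental use | 40% / 25% | 50% / 20% |

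A pre-test ever user is by definition still an ever user in 8th grade. I therefore set the outcome to 1 for such students and kept the 35% and 10% totals. In a least-squares regression on arm and the four covariates, the arm coefficient retains about 74% of the bias with weak markers and 33% with strong ones. For the 10-point gap that is 2.5 × 0.74 = 1.85 and 2.5 × 0.33 = 0.8 points. With the SE unchanged, the false-positive rates are about 5.0-5.2%, 5.3-6.3% and 6.0-10.4% for gaps of 2, 5 and 10 points.

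**5. The other reading: pre-test as first repeated outcome.** A comparison of change in ever use leaves gap × (0.25 − pre-test risk difference). At a 10-point gap:

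- Weak: 0.10 × (0.25 − 0.04) = 2.1 points, or 84%.
- Strong: 0.10 × (0.25 − 0.12) = 1.3 points, or 52%.

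The two readings differ by 2.1 − 1.85 = 0.25 to 1.3 − 0.8 = 0.5 points at the largest gap, and by a fifth of that at a 2-point gap. Part of this difference arises because step 4 also uses susceptibility, peer use and parental use.

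**6. What could still be set in advance.** A cohort that enters 6th grade in fall 2019 has follow-ups in spring 2020, fall 2020, spring 2021, fall 2021 and spring 2022. Three of the five were scheduled before the version date of 7/21/2021, and the protocol describes data analysis as ongoing from Year 2.

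**The case for a change.** The best case for a change runs as follows. The sequence is a recognised weakness of cluster trials. The protocol has no rule for choosing the 80 students in each school and no commitment to report consent by arm, so a reader could not check for selection. A short specification using data already collected would fix the primary model before the 8th-grade outcomes are analysed, at little cost.

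The facts in this argument stand, and so does the point that adjustment is incomplete: on the assumed inputs, a third to three quarters of any bias remains. The remedy gains little, however.

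- It names covariates for an adjustment to which the plan is already committed. The choice left open is guided by baseline data, not outcomes, and the obvious candidates are in the survey.
- Using the pre-test as a covariate or as the first repeated outcome is a choice between two legitimate models. The count of six measurements, read with level 1 of the three-level model, leans towards the second.
- Most follow-up waves were already scheduled before this version, which weakens the claim that the model would be set in advance.
- Pre-test ever use would predict later ever use almost perfectly and may not be estimable in a logistic model. Restricting to never users changes the analysed population, so naming this covariate raises a further choice.
- Consent counts and baseline risk by arm, and a statement of who knew the arm, belong in the trial report. They do not alter the analysis.

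**Conclusion.** No change to the plan is needed. Consent after randomisation, no described withholding of the arm and unnamed covariates are correct observations, but together they amount to missing detail that a competent analyst fills sensibly from variables the plan already collects. Differential consent is a possibility only. The common consent route, and a packet that covers measures completed in both arms, count against it; what families knew about the arm cannot be settled from this copy.

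The practical effect runs from negligible at gaps of 2 to 5 points in the higher-risk share to moderate at 10 points. Those results rest on assumed risk levels, ICC and marker strengths, on ever use persisting, on a linear model in place of the planned multilevel one, and on an unchanged standard error. A true gap of 10 points would be a reason for caution in interpretation, and naming the covariates beforehand would not cure it.

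### Ever use can change only once, yet it shares susceptibility's student-level model; with a logit or probit link its arm coefficient is either not finite or set largely by recanting

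*Combined protocol and SAP*

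**What the plan says.** Under Statistics, (2) Analysis of Hypothesis 1, susceptibility and ever use are treated in one paragraph with one model. The plan states "Three-level hierarchical models will be used to assess the impact of the intervention where level 1 is the repeated measurement of individual students", and continues "level 2 is the student, and level 3 is the school". The second outcome is given there as "b) ever e-cigarette use prevalence compared to students in the comparison schools".

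The outcome itself is first use. Aim 1 (Objectives) is to "Quantify the direct program effect on susceptibility and first use of e-cigarettes". Hypothesis 1 has "b) lowered first time (ever) use of e-cigarettes", and Background Information speaks of the programme's impact "on initiation of e-cigarette use (ever use").

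Under (3) Analysis of Hypothesis 2, the mediators are to explain "the effect of the intervention on the two primary outcomes (susceptibility and ever use"), and those analyses "will build on the multi-level models developed for the analyses described in Aim 1".

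The plan does not name a link function, the form of time, an effect measure or a fitting method. It also does not say how to code a student who reports use at one survey and denies it at a later one. The Data Collection and Management paragraph says that inconsistent answers are looked for, not what is then done with them. No separate model is given for ever use.

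**The concern.** A student random intercept describes a standing tendency around which answers vary from survey to survey. That suits susceptibility, which can rise and fall. Ever use, reported consistently, is a run of no's followed by a run of yes's. A logit or probit model with a finite student standard deviation (SD) always gives some probability to a yes followed by a no. When no such pattern occurs, the fit keeps improving as the student SD grows. The arm coefficient is on the same scale, so it grows too.

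At stake is the size of the effect on a primary outcome that Aim 1 sets out to quantify. The printed coefficient could not be read as a programme effect, and the ever-use mediation models would inherit it.

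**Working it through.** **The plan's own figures.** 30 × 80 = 2,400 students, 15 × 80 = 1,200 per arm and 1 + 5 = 6 surveys; all agree. The plan gives no ever-use rate, ICC, effect size or power, so the rates below are assumptions.

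**Assumptions.** Baseline never users: 0.95 × 1,200 = 1,140 per arm. There are five follow-ups. First use by spring of 8th grade is 15% (control) versus 10% (intervention), at constant hazard, so cumulative risk at wave k is 1 − 0.85^(k/5) or 1 − 0.90^(k/5). The population-averaged odds ratio is (0.10/0.90)/(0.15/0.85) = 0.63.

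**Logit link, consistent reports.** The model is logit P(yes at wave k) = wave effect + β × arm + student intercept with SD σ. The likelihood was integrated on a fine grid and maximised at fixed σ:

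| σ | log-likelihood | exp(β) | β/σ | standardised final risk |
|---|---|---|---|---|
| 5 | −1458.3 | 0.27 | −0.26 | 14.4% v 9.5% |
| 10 | −1354.7 | 0.086 | −0.25 | 15.0% v 10.0% |
| 20 | −1319.1 | 0.0085 | −0.24 | 15.0% v 10.1% |
| 40 | −1311.7 | 0.00008 | −0.24 | 14.9% v 10.1% |

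The log-likelihood is still rising at the last step. The odds ratio runs towards zero, while β/σ and the risks settle.

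**Sensitivity to the assumptions.**
- With equal increments per wave instead of constant hazard, the odds ratio again goes from 0.27 to 0.0001.
- With six waves, 1,200 per arm and 22% versus 16.5% at the end, the log-likelihood rises from −3447.6 (σ = 1) to −1988.77 (σ = 100), and the odds ratio falls from 0.645 to 2 × 10⁻⁹.
- With a probit link, the coefficient goes from −0.32 (σ = 1) to −6.49 (σ = 30).
- In a simulated three-level data set with school intercepts, the odds ratio falls from 0.26 to 0.00007 over σ = 5 to 40, while the likelihood-ratio chi-square for arm stays at 5.8 to 5.9.
- With no time term the estimate is finite (odds ratio 0.36 in the six-wave case). The divergence therefore depends on wave effects or a linear time trend being in the model.

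**Logit link, some recanting** (15% versus 10%, two-level):

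| reversal of later reports | fitted σ | odds ratio | arm chi-square | standardised risk |
|---|---|---|---|---|
| 2% | 14.0 | 0.036 | 12.8 | 14.4% v 9.7% |
| 5% | 10.2 | 0.088 | 12.8 | 13.9% v 9.4% |
| 10% | 7.8 | 0.156 | 12.8 | 13.2% v 8.8% |

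Initiation is the same in every row. Any coding rule that removes the reversals (once yes always yes, last answer wins, or dropping inconsistent students) restores the divergence.

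**Identity link.** The coefficient is finite, but two points arise.
- A single arm effect is the average over waves. The differences are 1.11, 2.17, 3.16, 4.11 and 5.00 points, with mean 3.1, against 5.0 in 8th grade.
- With arm-by-wave terms and random intercepts only, the model assumes equal variance at every wave, while the variance of ever use grows with prevalence. At 12.5% risk, 76 students per school and ICC 0.01, the true standard error is √(2 × 0.125 × 0.875/1,140 × (1 + 75 × 0.01)) = 1.83 points (about 1.82 in simulation). The model reports about 1.33. With a t reference on 28 df, the critical value 2.05 becomes 2.05 × 1.33/1.82 = 1.50 in true standard errors, a two-sided error of about 14%. Simulation also gives about 14%.

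**The case against.** The strongest reply is that the plan never promises an odds ratio and names no logit or probit link. It says the models will test for intervention effects, and the hypothesis concerns 8th-grade prevalence. The test and the standardised risks are stable, and those risks could satisfy Aim 1. This stands as a limit on the point. It does not remove it: a logit link is the ordinary choice for a yes/no outcome, its printed coefficient is what would normally be reported, and nothing in the plan steers the analyst to standardised risks.

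Second, real students recant, so estimates will be finite. That is true, but the estimate then tracks the recanting.

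Third, an identity link avoids the divergence, and the plan does not rule out random time slopes. This also stands. With slopes at student and school level, simulated type I error was 3.5% to 4.5% across ICCs of 0.005 to 0.02. The 14% applies to random intercepts alone.

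A reader might infer three stronger things that the documents do not support:
- *That the logit or probit p-value is invalid.* The arm chi-square is steady in the table above and in the three-level fit.
- *That numerical integration would hide or exaggerate a real effect.* The plan names no software or method. A comparison on 20 simulated trials is too small to settle it, and its reference method itself exceeded 3.84 in 5 of 20 no-effect sets.
- *That the link and coding rule will be chosen after the data are seen.* The plan is silent on these choices. Silence does not show when they are made.

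**Conclusion.** The point holds as a should-fix matter of analysis choice. Read with a student random intercept, a logit or probit link and wave effects, the stated model gives no finite arm coefficient for ever use when reports are consistent, and one set largely by recanting and its coding when they are not. The divergence comes from the shape of the data and appeared under every set of rates tried. The particular odds ratios depend on the assumed 15% versus 10% and on independent reversal.

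The damage is confined to the effect estimate, its interval and the mediation models that rest on it. The arm test and the 8th-grade risks survive accurate fitting. Under an identity link the problem is a different one: a standard error about a quarter too small (1.33/1.82 = 0.73) with random intercepts only, at an assumed ICC of 0.01.

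**What to change.** Keep the three-level model for susceptibility. For ever use, specify a model with no student random effect, in one of two forms:

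- a school-clustered model of ever use by spring of 8th grade; or
- a discrete-time hazard model of first use among baseline never users, using all waves.

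In either case:

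- Name a small-sample cluster correction suited to 15 matched pairs. In simulation with pair indicators, an uncorrected school-level sandwich variance gave 20.9% type I error with a z reference. A Kauermann-Carroll correction gave 4.9%, and a pair-level variance with t on 14 df gave 5.0%. Others may serve.
- Report the 8th-grade risk in each arm and the risk difference with its confidence interval.
- State that an earlier report of use is not cancelled by a later denial, with a sensitivity analysis under another rule. Baseline ever users are then yes by definition, so individual baseline use cannot be a covariate in a model that includes them.
- Say how students without a final survey are handled. They must not be counted only when an earlier answer was yes. With 20% missing, that turns 15% into (0.8 × 15 + 0.2 × 12.19)/(80 + 0.2 × 12.19) = 14.44/82.44 = 17.5%, and 10% into 9.62/81.62 = 11.8%.
- Build the ever-use mediation models on the risk scale.

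The cost is a second model form and SAP wording; the same six surveys suffice. Using only the final wave loses some information. At 15% versus 10%, ICC 0.01 and no gain from matching, simulated power is 71% with complete data and 65% if 20% miss the final survey and are left out. The hazard model, which keeps all waves, also has 71% with complete data.
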